C2. Study design. Participants will be randomly assigned to SBT or ABBT. Treatment will be delivered in 75-minute, small (12-15 participants), closed-group sessions. Groups will be held weekly in months 1-3, biweekly in months 4-6, and monthly in months 7-12, for a total of 25 sessions. Assessments will occur at months 0 (baseline), 1 (midpoint 1), 3 (midpoint 2), 6 (midpoint 3), 12 (post-treatment), and 24 (1-year follow-up).

C3. Alternative designs considered. While we considered a shorter treatment duration (to reduce burden and increase disseminability), we ultimately chose a 25-session treatment for three reasons. First, 25 sessions over 1 year is about the modal length and the recommended intensity for gold standard weight loss treatment. Second, this length is consistent with the increasingly-supported chronic care model of obesity.¹⁵⁷ Third, clinical trial experts have recommended that, for initial tests of efficacy, treatments should be evaluated at full potency to reduce the likelihood that failure occurs because of sub-optimal dosage.¹⁵⁸ If ABBT improves weight loss outcomes for BED, methods for reducing the intensity (e.g. optimization and refinement of session content) and increasing the scalability (e.g. use of alternative delivery methods and/or non-experts clinicians, both of which have been successfully completed with ABBTs for other disorders¹⁵⁹) can be explored in future studies. We also considered including a second follow-up assessment, but determined that given the time needed to recruit and treat 130 participants with BED, a longer follow-up period would not be feasible.

Timeline	Year 1			Year 2			Year 3			Year 4			Year 5			R = recruitment
Manual refinement	X	X														
Therapist training	X															A = assessment (A ₁ , A ₂ , A ₃ , A ₄ , A ₅ = months 0, 3, 6, 12, 24, respectively).
Wave 1	R	A ₁	A ₂	A ₃		A ₄			A ₅							
Wave 2		R	A ₁	A ₂	A ₃		A ₄			A ₅						
Wave 3			R	A ₁	A ₂	A ₃		A ₄			A ₅					
Wave 4				R	A ₁	A ₂	A ₃		A ₄			A ₅				
Wave 5					R	A ₁	A ₂	A ₃		A ₄			A ₅			
Wave 6						R	A ₁	A ₂	A ₃		A ₄			A ₅		
Data analysis														X	X	
Manuscript preparation														X	X	
Planning future studies, e.g. optimization														X	X	

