SBT techniques. During Phase 1, patients will be taught many of the same behavioral strategies described in the SBT section above to assist in meeting their calorie goals (e.g., self-monitoring of calorie intake; stimulus control techniques; problem solving skills). While many techniques will be similar to SBT, some modifications will be made to address the unique needs of patients with BED. For example, patients will receive education about the ways rigid dietary restraint can trigger binge episodes (e.g., severe caloric restriction, hedonic restriction, avoiding specific food groups, going long periods of time without eating), and will learn how to reduce caloric intake in ways that will minimize hunger and cravings. The table to the right provides examples of these strategies. One core difference will be that patients in ABBT will be encouraged to incorporate portion controlled palatable foods regularly to avoid feelings of deprivation that could trigger binge eating. While avoiding highly palatable foods can be a successful strategy for many obese patients, hedonic deprivation may be less sustainable for patients with BED and could encourage future binge eating or overeating episodes.

The exercise progression in ABBT will be the same as in SBT, with specific session content dedicated to psychoeducation about the benefits of physical activity for BED in Session 8. The ABBT treatment will also

provide psychoeducation relevant to patients with BED (e.g., session content on avoiding compensatory and compulsive exercise). We chose to begin the exercise progression in Phase 1 because 1) this will allow patients who are currently sedentary time to safely build up to the recommended exercise progression, and 2) research indicates that exercise can indirectly reduce binge eating episodes by improving depression, self-efficacy, and body image as well as reducing the degree to which binge eating episodes are used to regulate emotions.¹¹⁷ We considered using a more intensive exercise progression for ABBT, but decided that given the low long-term adherence rates observed in SBT⁹⁰⁻⁹⁴, the feasibility of meeting even higher activity goals would be limited.

Phase 2 (sessions 9-19): Phase 2 will focus on the use of acceptance-based strategies to improve adherence to dietary and physical activity goals and address shared maintenance factors for binge eating and overeating episodes. Below we will review how acceptance-based techniques will be incorporated in Phase 2.

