Distress tolerance. ABBT will help participants recognize that, 1) eating-related distress (e.g. urges to binge, hunger, cravings) is bound to occur in today's obesogenic environment, particularly given the elevated food reward sensitivity common in BED and 2) attempts to avoid these internal experiences are often ineffectual or even counterproductive. Participants will learn to tolerate aversive states related to eating (e.g., cravings) and physical activity (e.g., boredom, discomfort) while continuing to engage in the desired behaviors through in-session experiential activities and at-home practice. For example, in one session, participants will hold themselves in the "plank" (an unsupported sitting) position and practice tolerating the bodily discomfort that is generated by this exercise. ***Willingness*** (simultaneously engaging in a valued action while accepting the discomfort it generates) will be framed as more adaptive than distress *intolerance* (i.e., eating foods or ceasing/avoiding activity to avoid being uncomfortable). Experiential exercises will allow participants to practice distancing themselves from thoughts and feelings in a way that enhances willingness to experience them, thereby reducing the necessity of acting (e.g., ending a walk early, eating a chocolate bar) to alter the experience. Unlike SBT, ABBT assumes that attempts to distract from or modify thoughts and feelings are rarely productive; rather, long-term adherence to health behaviors depends on the ability to tolerate unpleasant internal experiences. Distress tolerance will also be used to address elevated negative affect that contributes to binge eating and overeating episodes. Reductions in binge eating have been mediated by changes in distress tolerance, supporting its importance as a treatment target in BED.¹⁸⁰ Patients will be taught how to tolerate negative affect without using food as a way to distract from or numb out uncomfortable experiences.

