C9. Assessments and Measures. Assessments will occur at the start of treatment (baseline), 1 month (midpoint 1), 3 months (midpoint 2), 6 months (midpoint 3), 12 months (post-treatment), and 24 months (1-year follow up). All outcome and process measures described below will be completed at each assessment. Acceptability will be assessed at post-treatment. All assessments will be completed onsite in Drexel University's Department of Psychology. Efforts will be made to schedule midpoint assessments directly after or directly before a treatment session to reduce participant travel burden (e.g. month 3 assessment will occur between sessions 12 and 13, with effort made to schedule participants right after session 12 or right before session 13 if possible). All assessments will be conducted by blind raters (graduate students who will be highly trained and closely supervised by [name]). Blind raters will receive training on standard procedures for collecting anthropometric data and administering all process measures described below. Raters will be required to pass a "mock" assessment with [name] and reach 100% agreement on eating disorder diagnosis and acceptable reliability (>.80) on EDE scoring before they will be cleared to conduct assessments.

Feasibility and Acceptability. Assessment of feasibility will include number of patients screened per month, % of eligible patients enrolled, treatment attrition (% of patients that prematurely terminate treatment), study retention (% of patients that complete all assessments), treatment adherence, and treatment fidelity. Acceptability will be assessed using the Feedback Questionnaire and Credibility/Expectancy Questionnaire¹⁹⁴ to gauge participant's attitudes and feelings toward the treatment.

Outcomes. The primary outcome measure for the study will be change in **weight**. Weight will be measured in street clothes without shoes using a standardized Secca® scale accurate to 0.1 kg. **Eating pathology** will be a secondary outcome measure and will be measured by The Eating Disorder Examination (EDE), a widely utilized, semi-structured interview for eating disorder symptoms.¹⁹⁵ Participant's EDE global scores and objective binge frequency will be the primary outcome measures for eating disorder pathology.

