A Negative Mood Induction (NMI) task will be used to assess **negative affect** and **distress intolerance** during and after an acute stressor. Following completion of all study measures participants will undergo an autobiographical recall task, a commonly used negative mood induction.²⁰⁶⁻²⁰⁸ Mood will be assessed using the Short Positive and Negative Affect Scale (PANAS)²⁰⁹ before and after the mood induction and after a ten-minute waiting period following the mood induction. Heart rate (a physiological measure of emotional state)

will be monitored throughout the induction and post-induction period using the Polar E600 heart rate monitor. Several prior studies have utilized mood inductions to assess ability to regulate and tolerate negative emotions in response to a stressor.²¹⁰⁻²¹³ Distress intolerance will also be measured using the Difficulties in Emotion Regulation Scale (DERS).²¹⁴ The DERS assesses awareness and understanding of emotions, ability to tolerate emotional arousal, and effective action in the presence of intense emotions. We will also use two behavioral measures of distress intolerance. The computerized Mirror-Tracing Persistence Task^{215, 216} measures the amount of time a participant is willing to engage in a frustrating task (tracing a dot on a computer screen that moves in the opposite direction as one moves the computer mouse). The cold pressor test measures the length of time a participant is willing to leave her hand in water kept at 3°C through the use of a circulating water bath system (Lauda RM6) For safety reasons, participants are not allowed to exceed 300 sec of exposure to the cold water.²¹⁷ Both of the aforementioned behavioral tasks have proven valid measures of distress tolerance in health behavior areas, particularly smoking cessation.^{216, 218-223} Lastly, depressive symptoms will be assessed using the Beck Depression Inventory-II, a 21-item measure assessing levels of depressive symptomatology.²²⁴ This self-report scale is widely used and has proven reliable across a variety of demographic groups and in both clinical and nonclinical populations.

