For Secondary Aim 1, mediation analyses were conducted using the R “lavaan” structural equation modeling package (Rosseel, 2012). Mediation analyses estimated the indirect effect of treatment condition through change in each mediator from baseline to 3-months on percent change in weight, binge eating frequency change, and global eating disorder psychopathology change at post-treatment and through changes from baseline to 6-months on weight, binge eating frequency change, and global eating disorder psychopathology change at one year follow-up. Baseline levels of the dependent variable and mediator were included as covariates in mediation models. Physical activity minutes and VLQ scores were z-score normalized to correct for significantly larger variances.

References

Knowles, J. E., Frederick, C., Whitworth, A., & Knowles, M. J. E. (2023). Package 'merTools'.

Rosseel, Y. (2012). lavaan: An R package for structural equation modeling. *Journal of statistical software*, 48, 1-36.

Selya, A. S., Rose, J. S., Dierker, L. C., Hedeker, D., & Mermelstein, R. J. (2012). A practical guide to calculating Cohen's f^2 , a measure of local effect size, from PROC MIXED. *Frontiers in Psychology*, 3, 111.

Van Buuren, S., & Groothuis-Oudshoorn, K. (2011). mice: Multivariate imputation by chained equations in R. *Journal of statistical software*, 45, 1-67.

Wing, R. R., Tate, D. F., Gorin, A. A., Raynor, H. A., & Fava, J. L. (2006). A self-regulation program for maintenance of weight loss. *New England Journal of Medicine*, 355(15), 1563-1571.

Zhang, Y. W. (2013). CPLM: compound Poisson linear models. *A vignette for R package cplm*. Available at <http://cran.r-project.org/web/packages/cplm>, 619, 621.

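### Month-3 and month-6 assessments may fall straight after a session, so state-sensitive mediator measures could carry a short-term after-session effect in ABBT only

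*Protocol*

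**What the plan says.** On timing, Protocol C9 states: "Efforts will be made to schedule midpoint assessments directly after or directly before a treatment session to reduce participant travel burden". Its month-3 example places the visit between sessions 12 and 13, "with effort made to schedule participants right after session 12 or right before session 13 if possible". The only reason given is travel. No text prefers one side of the session, balances the choice by arm, sets a minimum gap, or says that the timing is recorded.

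On content, C9 adds: "All outcome and process measures described below will be completed at each assessment". The process measures include mirror-tracing persistence, a cold-pressor test that "measures the length of time a participant is willing to leave her hand in water", and PANAS mood ratings and heart rate around a negative mood induction. They also include questionnaires such as the DERS.

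On treatment, C6b describes "Phase 2 (sessions 9-19): Phase 2 will focus on the use of acceptance-based strategies". Its distress-tolerance paragraph includes a plank exercise in which participants "practice tolerating the bodily discomfort that is generated by this exercise". The component list for SBT in C6a has no counterpart.

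On analysis, Protocol C10 (Secondary Aim 1) lists negative affect and distress tolerance among the mediators. The SAP estimates mediation through change from baseline to 3 months for post-treatment outcomes, and "through changes from baseline to 6-months on weight, binge eating frequency change, and global eating disorder psychopathology change at one year follow-up". The only covariates it names for these models are the baseline values of the outcome and the mediator.

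**The concern.** How long someone keeps a hand in cold water, persists at a frustrating task, or reports low mood can depend on what happened shortly beforehand. An ABBT participant tested straight after practising how to stay with discomfort may show short-term priming or compliance as well as lasting change. An SBT participant tested at the same point has had no such practice, so this component would not cancel between arms.

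Secondary Aim 1 looks for durable change in the mediator that precedes later outcome. A transient shift present only in ABBT would enlarge the path from treatment to mediator without being the mechanism sought. The visits open to this are the two from which the SAP takes its mediator change.

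**Working it through.** The plan gives no figure on this point to reproduce. The check is whether the structure holds in the text, and then what size would follow under stated assumptions.

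**1. Which sessions adjoin months 3 and 6?** C2 states: "Groups will be held weekly in months 1-3, biweekly in months 4-6, and monthly in months 7-12, for a total of 25 sessions". Twelve weekly, six biweekly and six monthly sessions give 12 + 6 + 6 = 24. The stated 25 is reached by 13 + 6 + 6 or 12 + 7 + 6. Month 3 adjoins session 12 by C9's own example. By month 6 the count is 12 + 6 = 18, or 13 + 6 = 12 + 7 = 19.

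**2. Which ABBT phase is that?** Phase 2 covers sessions 9-19, so both visits can follow a Phase 2 session. Month 1 adjoins about session 4, in Phase 1 (sessions 1-8). The point is therefore confined to months 3 and 6.

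**3. Can baseline adjustment remove it?** No. Under C5 the baseline assessment precedes randomisation, so it adjoins no session and carries no information about an after-session shift.

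**4. Size of the bias on the mediator.** Let p be the share of an arm tested straight after a session and s the acute shift in SD units. The bias in the arm difference is p(ABBT) × s(ABBT) − p(SBT) × s(SBT). For the tolerance-practice component take s(SBT) = 0, leaving p × s. Neither value is in the documents. Assume p = 0.3-0.7 and s = 0-0.5 SD:

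- lower end: any p × 0 = 0
- p = 0.5: 0 to 0.5 × 0.5 = 0.25 SD
- upper end: 0.7 × 0.5 = 0.35 SD

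The formula also shows that any general session effect, such as fatigue, cancels only if the after-session share is the same in both arms, which C9 does not secure.

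**5. Consequence for the indirect effect.** A single-mediator model was simulated with no lasting ABBT effect on the mediator, an assumed mediator-to-outcome slope of 0.26, 1:1 allocation, two-sided 0.05 tests of both paths, and 4,000 runs. This is a simplified stand-in for the SAP's model. A transient shift with no effect on outcome was added for a share of ABBT participants. The sample sizes are the 104 and 130 of C11. The entries are the percentage of runs with a falsely significant indirect effect:

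| Share after session | Shift (SD) | N = 104 | N = 130 |
|---|---|---|---|
| 0 | 0 | 3.4% | 3.5% |
| 0.5 | 0.2 | 5.4% | 6.9% |
| 0.5 | 0.5 | 17.6% | 21.9% |
| 1 | 0.2 | 11.8% | 16.3% |
| 1 | 0.5 | 52.0% | 65.7% |

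The mean spurious indirect effect is about share × shift × slope. For the third row this is 0.5 × 0.5 × 0.26 = 0.065, against 0.063 simulated at N = 104. The last two rows need every ABBT participant to be tested after a session, which C9 does not imply.

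**The case against.** The strongest reply is that the acute effect is conjecture. Neither document reports a short-term session effect on any of these measures, and its size, sign and existence are all assumed. This stands, and it is why the range above starts at zero.

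Several further points also stand:

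- The plank exercise belongs to one unidentified session. Phase 2 also covers values and commitment work, and no text places tolerance practice in session 12, 18 or 19.
- The SAP refers to each mediator without listing instruments and names only physical activity and the VLQ. Protocol C10 names constructs. Distress tolerance could enter the models through the DERS, a questionnaire that may be less state-dependent, rather than through the cold pressor or mirror tracing.
- The mood induction follows the other study measures, so some delay is built in, and PANAS is also taken before the induction.
- Scheduling next to a session is only an aim, the before-session slot is allowed, and the SAP shows that some groups met by telehealth. Exposure is probably diluted.
- A transient shift yields a spurious indirect effect only if the mediator also predicts outcome. At a half share and 0.2 SD the false-positive rate moves only from 3.4% to 5.4% at N = 104.

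What the reply does not meet is the structural point. Two different measurement conditions are allowed at the mediator visits, the arms differ in what may precede them, and nothing in the design or the SAP models controls for it.

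**Conclusion.** The point holds as a possible arm-specific measurement artefact that the schedule leaves open. Under the assumed share and shift it biases the arm difference on distress tolerance or negative affect by 0-0.35 SD, and the effect on mediation tests runs from negligible to serious. It touches Secondary Aim 1 and the process-measure contrasts only; the primary weight analysis does not depend on it.

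A reader might infer that the mediation results are in fact biased, or that a definite fraction of any mediator signal is artefact. The documents support neither, because they give no acute effect, no after-session share and no expected arm difference in SD for these measures. A reader might also infer that raters would be unblinded, or that a fall from month 6 to month 12 would be misread. The first needs raters to know which arm meets when, which is not stated; for the second, the SAP describes no analysis of that change.

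This is a worthwhile low-cost improvement rather than a defect that undermines the trial.

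**What to change.** For any visits still to come, or reuse of the design, amend C9 so that midpoint assessments are held directly before a session or on a non-session day, never directly after one, under the same rule in both arms. One sentence suffices, and the travel saving is largely kept. The cost is fewer same-day slots, so some participants move to another day.

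The SAP is written in the past tense, so for completed visits the remedy is analytic:

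- Where timing was recorded, classify each month-3 and month-6 visit as before a session, after a session or another day, and report the split by arm.
- State which instruments represent distress tolerance and negative affect in the mediation models.
- Repeat those models either adjusting for timing or omitting after-session visits. Since the suspected shift is in ABBT only, the adjustment needs an arm-by-timing term; a common timing term would not isolate it.

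Timing is a post-randomisation variable, so this is a sensitivity analysis and not a replacement. Omission also costs sample. At the assumed shares applied to both arms, 130 × (1 − 0.3) = 91 down to 130 × (1 − 0.7) = 39 would remain before attrition, against the 130 that C11 gives for 80% mediation power. Compare the estimates and intervals rather than whether significance is kept. If timing was not recorded, say so as a limitation of the mediation findings.

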Primary Aim (Efficacy of ABBT). Analyses will be conducted via linear mixed effects models for longitudinal data, which increase power by fully exploiting the strong correlation in treatment outcomes of interests (i.e., primarily, percent weight loss and secondarily, percent binge frequency reduction) across time. Patterned covariance matrices as implemented in SAS/STAT PROC MIXED V9.2 will be used to evaluate between group differences for percent weight loss and percent binge reduction across the study as a whole, and at each assessment post-baseline.²²⁵ Separate variance components will be used to capture therapist and participant-within-therapist variation. The within-subject covariance matrix will be assumed common across study arms, with an exponential variance function to deal with heteroscedasticity and a continuous-time AR(1) correlation matrix to accommodate residual autocorrelation over the unequal-size time intervals between follow-ups. Outcomes at all six time points will be estimated jointly for maximum statistical efficiency in the presence of intermittent missingness and loss to follow-up. The model will include random effects for subject and time (with higher-order effects if needed to capture nonlinear change), and fixed effects for treatment arm, time by treatment interaction, demographic information, and baseline values of weight, dietary intake and physical activity. Time-specific covariate-adjusted contrasts will be used to compare outcome between groups.

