Primary Aim (Efficacy of ABBT). The study's data will consist of repeated assessments over time within randomized individuals within each treatment condition. Therefore, power calculations are dependent on both an expected difference between treatment arms as well as the clustering of the data (repeated observations within an individual with up to six repeated measures per participant within one of the two treatment conditions), resulting in a multilevel model structure. Using the method described by Raudenbush²⁵²⁻²⁵⁴ and implemented with the software Optimal Design, power calculations were made for this multilevel model structure. No results are available which directly compare the effect of ABBT and SBT on weight loss in BED patients. However, effect size can be predicted by deriving effect sizes from trials with elements similar to the proposed study, e.g., percent weight loss comparison between ABBT and SBT from the Mind Your Health II study (effect size at 12 months $d=0.39$) and percent weight loss and binge reduction comparison of CBT vs. SBT ($d=0.625$; 30% difference in binge reduction rates).⁶⁴ Based on previous studies, we aim to detect a clinically meaningful difference for both weight and binge eating frequency (3.5% weight loss between groups ($d=0.46$) and a difference in 4 binge eating episodes over the 4-week time period). Baseline covariates that can account for variability in the trial outcomes were taken into consideration in the power analysis. Given these assumptions, a sample size of 104 (52 for each group) is required for 80% power with the significant level of 0.05 and five assessment points, assuming the ratio of the variability of level-1 coefficient to the variability of level-1 residual is one. While allowing for up to 20% attrition, the proposed sample size of 130 is adequately powered to examine a clinically meaningful difference between treatment conditions for both percent weight loss and frequency of binge episodes. We believe this power estimate to be conservative given: 1) attrition estimates are greater than the team has achieved in similar weight control studies; and 2) missing values will be imputed using multiple imputation to maximize the number of the observations used to estimate models.

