Mixed effects models were conducted for Primary Aim 1 (Efficacy of ABT) and Secondary Aim 2 (Between-Subjects Moderation) given nested data within subjects and group. The R “merTools” package was used for models predicting percent weight change and global eating disorder psychopathology change (Knowles et al., 2023), and the R “cplm” package was used for models predicting binge eating frequency change (due to zero-inflated distribution of percent binge eating change at post-treatment and follow-up) (Zhang, 2013). Models for percent weight and binge eating change included fixed effects for the interaction between linear or quadratic time effects and treatment condition (and baseline moderators for Secondary Aim 2). Only linear time effects were included in the models for global eating disorder psychopathology, since the quadratic time fixed effect did not significantly improve model fit. Model selection criteria (e.g., Aikaike information criteria, Bayesian information criteria) and significance testing were used to identify the random effects structure that best fit the model. For percent weight change, models included separate random effects for intercept and slopes of quadratic time effects nested within subjects. For binge eating frequency change, models included random effects for intercept nested within subjects. For global eating disorder psychopathology change, models included separate random effects for intercept and slopes of linear time effects nested within subjects. No differences in results were observed when treatment format delivery (i.e., telehealth vs. in-person groups) was included as a covariate; therefore, results without the inclusion of treatment format delivery as a covariate are reported. Statistically significant interactions were interpreted by plotting simple regression lines for each variable. For all linear mixed effects models, alpha was set at 0.05 and confidence intervals were obtained. Cohen’s f^2 effect size measures were estimated for group x time interaction using methods described by Selya and colleagues (Selya et al., 2012), with $f^2 \geq 0.02$, $f^2 \geq 0.15$, and $f^2 \geq 0.35$ representing small, medium, and large effect sizes, respectively.

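### Neither document says which comparison of percent weight loss decides efficacy, or controls for testing it overall, at five visits and through time-by-arm terms

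*Protocol*

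**What the plan says.** Protocol C9 (Outcomes) states that "The primary outcome measure for the study will be change in" weight and gives no time point. C9 also sets the post-baseline assessments at months 1, 3, 6, 12 and 24.

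Protocol C10 (Primary Aim) fits a longitudinal mixed model and evaluates differences between arms in percent weight loss "across the study as a whole, and at each assessment post-baseline". It adds: "Time-specific covariate-adjusted contrasts will be used to compare outcome between groups".

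In the protocol, a significance level for the primary aim appears only in the power section. C11 describes its sample size as "required for 80% power with the significant level of 0.05 and five assessment points". That section cites a 12-month effect size of d = 0.39 from an earlier trial as background and sets the design target at a 3.5-point difference (d = 0.46). Neither is tied to a particular test.

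The SAP, in the paragraph on mixed effects models, reads: "Models for percent weight and binge eating change included fixed effects for the interaction between linear or quadratic time effects and treatment condition". It also says: "For all linear mixed effects models, alpha was set at 0.05 and confidence intervals were obtained". It does not say which interaction term decides efficacy and mentions no visit-specific contrasts. Neither document gives a testing order, a success rule or a multiplicity adjustment.

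**The concern.** The protocol sets six comparisons of the primary outcome side by side, with 0.05 as the only level in sight. A claim that ABBT is superior could then rest on whichever comparison is significant, and the chance of a false claim would exceed 5%.

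The SAP shortens the list but leaves the question open. It does not say whether the linear term, the quadratic term or both together carry the claim. It also leaves out the time-specific contrasts that the protocol promised. A quadratic-by-arm term describes a difference in curvature. On its own it does not tell the reader which arm had lost more weight at the end of treatment or at follow-up.

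**Working it through.** **Figures in the plan.** The documents state no familywise error rate, so there is none to reproduce. The enrolment figure does follow from its inputs: 104 / (1 - 0.20) = 130.

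**Inputs from the documents.** Five post-baseline visits plus one overall comparison give 6 tests (C9, C10). Alpha is 0.05 (C11, SAP), taken as two-sided because sidedness is not stated. There are 52 per arm and d = 0.46 (C11).

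**Assumptions.** (a) Any significant comparison counts as success. (b) The between-visit correlation is varied over a range, because C10 calls it strong without giving a number. (c) The overall test is the average of the visit contrasts.

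**Step 1, upper bound for the protocol family.** With k independent tests the error is 1 - 0.95^k.
- k = 5: 1 - 0.95^5 = 22.6%
- k = 6: 1 - 0.95^6 = 26.5%

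**Step 2, correlated visits.** One million draws of five correlated z-statistics under no effect, counting a trial as a success if any |z| > 1.96:

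| Assumed correlation | Any of 5 visits | Visits plus overall |
|---|---|---|
| Equal, 0.3 | 20.9% | 21.4% |
| Equal, 0.5 | 18.2% | 18.4% |
| Equal, 0.7 | 14.8% | 14.8% |
| Equal, 0.9 | 10.2% | 10.2% |
| Equal, 0.95 | 8.5% | 8.5% |
| Continuous-time AR(1), 0.90 per month | 18.3% | 18.7% |
| Continuous-time AR(1), 0.95 per month | 15.4% | 15.5% |
| Continuous-time AR(1), 0.98 per month | 11.7% | 11.8% |

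C10 applies AR(1) to the residuals on top of random effects for subject and time. Adding a subject intercept with an assumed 30-70% share of the variance, and omitting the random time effect, changes the AR(1) rows to about 8.5-16%. Using a 5-df omnibus test as the overall test, with equal correlation, gives 11.4% (at 0.95) to 21.3% (at 0.3). The working range is therefore about 8-21%.

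**Step 3, SAP family.** Two uncorrelated tests give 1 - 0.95^2 = 9.75%. On months 0, 1, 3, 6, 12 and 24, ordinary least squares with raw time and time squared gives coefficient estimates correlated at about -0.96. Two z-tests with that correlation give about 6%. The range is about 6-10%, and only if both terms are tested separately.

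**Step 4, power of one visit contrast.** For a simple unadjusted comparison, the noncentrality is d x sqrt(n/2) = 0.46 x sqrt(26) = 2.35. A two-sided t-test with 102 df then has about 64% power. The normal approximation gives 65%. C11 took baseline covariates into account but gives no R-squared. In the simple formula, an assumed R-squared of about 0.30 brings power at 52 per arm to 80%.

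**Step 5, cost of full adjustment.** Bonferroni over six tests is 0.05 / 6 = 0.0083 each. At 52 per arm and d = 0.46, power per test falls to about 38% unadjusted, or 57% with R-squared 0.30. One deciding test is the better course.

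**The case against.** The strongest reply is that no inflated error rate follows from the text itself. C10 does not say that each visit contrast is a success criterion, or that each is tested at 0.05. If the overall comparison alone decided, the error would be 5%. That is right, and it is why the percentages above are conditional. It does not remove the point, because C10 lists overall and visit-level evaluation together and ranks neither.

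A reader might infer that the primary-aim error is about 12-19%. That range comes from AR(1) correlations of 0.90-0.98 per month with no subject effect, plus the any-test-wins rule. The documents supply neither the correlations nor the rule, and including the subject effect that C10 specifies lowers the figure.

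A reader might also carry the protocol's range over to the SAP. That is not supported. The SAP describes no visit tests, its wording does not establish two separate tests, and two tests cannot exceed 9.75% when the terms are uncorrelated and give about 6% on this schedule.

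It can also be said that the SAP points to the group-by-time interaction as the effect of interest. It gives an effect size for it, reports confidence intervals, and interprets significant interactions from plotted regression lines. This counts against any suggestion that visits were searched for a significant result. It still leaves the deciding term unnamed, and a plot is not an estimated difference at month 12 or 24.

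Finally, the trial was not sized on a month-12 contrast. The d = 0.39 is background, and the target is d = 0.46 in a repeated-measures calculation. This stands, and it is a real cost of the fix.

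**Conclusion.** The point holds as a gap with a conditional size. Neither document names the test that decides efficacy on percent weight loss or controls for multiple comparisons. If any of the protocol's six comparisons counted as success, type I error would be roughly 8-21% for between-visit correlations from 0.95 down to 0.3. If both SAP interaction terms were tested separately, it would be about 6-10%. Both ranges assume two-sided 0.05 for every test. With one designated test the error is 5%.

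Separately from the error rate, the SAP leaves out the protocol's time-specific contrasts, so its description does not give a direct estimate of which arm lost more weight at post-treatment or follow-up. The documents do not show that a claim was actually chosen from among several tests.

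**What to change.** - Make one 2-df joint test of the linear and quadratic time-by-arm terms, at two-sided 0.05, the single efficacy test of the SAP growth model.
- Report the model-based between-arm contrasts in percent weight loss at months 12 and 24, with confidence intervals. Month 12 (post-treatment) is the main contrast. Test month 24 only if month 12 is significant.
- Label all other visit-level, overall and single-term results as descriptive and unadjusted.
- Disclose that no deciding contrast was prespecified.

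The work is SAP wording, one joint test and two contrasts from a model already fitted, with no change to the sample size. There are three costs. An isolated early-visit or single-term result can no longer be claimed as primary. A single-visit contrast may have less power than the repeated-measures calculation (about 64% unadjusted at d = 0.46 with 52 per arm). And because the SAP is written in the past tense and already reports results, the designation is partly retrospective: it makes the reporting transparent but cannot fully restore prespecified error control.
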